Patients actively receiving therapy may be considered for intra-patient dose escalation to receive a dose level no higher than the highest dose that has previously been deemed safe and tolerable (and thus below the MTD) by the CRC, following review and approval by the Medical Monitor ([Section 3.1.1.4](#)).

During Dose Expansion, up to 20 additional evaluable patients will receive HPN424 at the RP2D(s) established in the Dose Escalation stage of the study.

HPN424 will be administered by either intravenous (IV) infusion or subcutaneous (SC) injection. All patients will be administered HPN424 once weekly (QW) during 21-day cycles. Pre-medications will be administered as indicated based on assigned cohort ([Section 5.1.4](#)).

Patients may continue to receive HPN424 treatment beyond disease progression provided there is clinical benefit (NLCB, per PCWG3 guidelines, ([Scher, 2016](#)) as determined by the Investigator and upon consultation with the Medical Monitor. Disease assessments (PSA, bone scans and CT/MRI) should continue irrespective of whether study treatment is missed or delayed.

3.1.1 *Part 1: Dose Escalation Study Design*

Dose escalation will be performed initially with single patient cohorts followed by a 3 + 3 design with two parallel arms (Fixed Dosing, Step Dosing) to evaluate tolerability of different dosing regimens:

- During single patient dose escalation and in the 3 + 3 dose escalation Fixed Dosing arm, patients will receive the Target Dose (the intended dose for a particular cohort) starting on Cycle 1 Day 1 and beyond.
- During step dosing, patients will initiate treatment with Priming Dose A on Cycle 1 Day 1. The Target Dose will be administered on Cycle 1 Day 8 and beyond.

- A second priming dose, Priming Dose B, may be implemented in the next cohort on Cycle 1 Day 8. In this case, the Target Dose will be administered on Cycle 1 Day 15 and beyond ([Section 3.1.1.2.2](#)).
- Additional Priming Doses may be added (e.g., Priming Dose C) based on the observed safety and tolerability ([Section 3.1.1.2.2](#)).

For safety reasons, a staggered start will be employed when a higher dose level cohort is opened. At least 48 hours must elapse between dosing of the first and second patient at any given dose level.

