3.1.1.5 Intrapatient Dose Escalation

Patients actively receiving therapy may be considered for intrapatient dose escalation to receive a dose level that is no higher than the highest dose that has previously been deemed safe and tolerable (and thus below the MTD) by the CRC, following review and approval by the Sponsor Medical Monitor.

The following criterion must be met to be considered for intrapatient dose escalation:

- Patients must have completed at least 2 cycles (6 doses) at their current dose level without intolerable toxicity.

All patients who undergo intrapatient dose escalation will receive premedication based on discussion between the Investigator and Medical Monitor and be hospitalized for 24-hour inpatient observation following the first of each escalated dose ([Section 5.1.4](#)).

See [Section 5.1](#) for provisions where intrapatient transition to a different route of administration may be appropriate.

[figure not shown]
[figure not shown]
3.1.2 *Part 2: Dose Expansion Study Design*

[figure not shown]
[figure not shown]
[figure not shown]
The CRC will determine the RP2D(s) (Priming Dose/Target Dose) regimen and preferred route of administration at or below the MTD. The RP2D(s) will be selected on the basis of available safety, clinical activity, and pharmacokinetics and pharmacodynamics data gathered during Dose Escalation.

Up to 20 evaluable additional patients will receive HPN424 at the RP2D(s) established in the Dose Escalation stage of the study. While the intention is to study a single RP2D, additional

expansion cohorts of up to 20 evaluable patients per expansion cohort may be added at the recommendation of the CRC.

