The non-GLP single dose PK study (Study 20133857 or HPN424PK-01) and a GLP-compliant toxicity study (Study 2012494 or HPN424TOX-01) as described in [Section 1.5](#), revealed a serum terminal half-life of approximately 3 days for HPN424 in cynomolgus monkeys. These findings support an initial dosing regimen of once weekly in humans.

3.3 *Study Duration and Dates*

Patient participation includes Screening (28 days), Treatment (ongoing in 21-day cycles), End of Treatment visit (within 7 days after the last dose of HPN424), and Safety Follow-up (SFU; 28 days [+ 7 days] after the last dose of HPN424), after which patients will enter long term follow-up (LTFU) for survival. Patients may continue weekly HPN424 treatment as long as they are receiving clinical benefit (as determined by the Principal Investigator and upon consultation with the Medical Monitor).

For purposes of estimating study duration, patients are expected to remain on treatment for approximately 28 weeks, making total study duration for each patient approximately 32 weeks through the SFU, or 18-24 months total including LTFU for survival. Given that patient recruitment is expected to occur over approximately 36 months, the study as a whole is expected to last approximately 48 months until the last patient completes the SFU.

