Late DLTs are AEs that meet the same grading criteria as DLT criteria and occur after the DLT period through the 60-day assessment period during Dose Escalation. At the time of the CRC meetings to review a specific cohort, the late DLT events for that cohort will be reviewed by the CRC ([Section 11.9](#)), which may decide to:

- Continue enrollment in higher dose level cohorts
- Increase the number of patients at the dose level in which the late DLT occurred to satisfy the 3 + 3 decision rules. All patients will be followed for at least 60 days to reassess safety at this dose level. If the 3 + 3 decision rule of dose-escalation is reached, enrollment in higher dose level cohorts may resume. If, after the enrollment of additional patients, the CRC recommends dose de-escalation, then all patients will be dose-reduced to the recommended dose level.
- Permanently stop enrollment in higher dose level cohorts and declare the dose level to be above MTD. Increase the number of patients at the dose level in which the late DLT occurred satisfy the 3 + 3 decision rules.
- Stop the study

For any patient that is being treated at a dose level that is subsequently considered to be above the MTD, the option to dose-reduce will be discussed. If a patient tolerated the above-MTD dose level well and is benefiting (as determined by the Principal Investigator and upon consultation with the Medical Monitor), continuation of treatment at the above-MTD dose level will require re-consenting.

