8.2 Treatment Period

Cycle 1 Day 1 predose assessments must be completed within 72 hours prior to the start of the Cycle 1 Day 1 dose of HPN424, unless otherwise indicated. If screening assessments were done within this window, they need not be repeated on Cycle 1 Day 1.

The timing of dose administration, hospitalization schedule ([Section 5.1.4](#)), and DLT observation period for each cohort is dependent on the assigned dosing regimen and treatment arm and detailed in [Table 15](#).

Table 15 Cycle 1 Treatment and Monitoring Schedule

	Fixed Dose Regimen	One Priming Dose Regimen (Prime A)	Two Priming Dose Regimen (Prime A + Prime B)	Three Priming Dose Regimen (Prime A + Prime B + Prime C) ^b
Priming Dose A	--	C1D1	C1D1	C1D1
Priming Dose B	--	--	C1D8	C1D8
Priming Dose C	--	--	--	C1D15
Target Dose	C1D1	C1D8	C1D15	C2D1
DLT Period	D1-D21	D1-D28	D1-D35	D1- D42
Hospitalization	C1D1, C1D8	C1D1 ^a , C1D8, C1D15	C1D1 ^a , C1D8 ^a , C1D15, C2D1	C1D1 ^a , C1D8 ^a , C1D15, C2D1, C2D8

^a Hospitalization for Priming and Target dose(s) may be reduced or omitted based on CRC review of the emergent safety data at a particular dose level (Section 5.1.4).

^b If additional Prime Doses are added (e.g., Prime Dose D) Cycle/Day for Prime Dose and first Target dose will be determined by the number of Priming doses for a given regimen (e.g., Priming Dose A will be administered on C1D1, Priming Dose B on C1D8, Priming Dose C on C1D15, and Priming Dose D on C2D1 and so on. The DLT period for all patients in a given cohort will be through 21 days after the first Target Dose.

The patient will be asked to complete scheduled visits and assessments per assigned dose regimen.

During the Treatment Period, disease assessments (including PSA and radiological imaging) are to be performed as indicated irrespective of whether treatment is delayed or missed. In other words, the schedule for these items is calendar-based and fixed relative to C1D1.

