10.7 Analysis of Safety

Safety summaries will include summaries in the form of tables and listings. For all patients, AE data will be listed by dose level cohort. The frequency (number and percentage) of treatment-emergent AEs will be summarized by system organ class and preferred term using the Medical Dictionary for Regulatory Activities (MedDRA). Summaries will also be presented by the severity of the AE and by relationship to study treatment. In addition, DLTs and all SAEs, including deaths, will be listed separately and summarized.

Laboratory shift tables containing counts and percentages based on NCI CTCAE (version 5.0) grade will be prepared by dose level cohort, laboratory parameter, and time. Summary tables will be prepared for each laboratory parameter. Figures of changes in laboratory parameters over time will be generated.

Changes in vital signs, ECGs, and ECOG scores will be tabulated and summarized.

Concomitant medications will be coded according to the World Health Organization (WHO) Drug Dictionary and listed.

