7 GENERAL DATA HANDLING CONVENTIONS

7.1 Data Display Characteristics

All data collected in EDC will be reported in by-patient data listings, including any derived variables. They will be sorted by cohort, patient number, and date/time of assessment. The data will include all patients in the database regardless of their receipt of study drug.

Part 1 of the trial has too many dose cohorts to reasonably fit on a single summary table. Since the primary goal of data review and reporting will be focusing on the major differences in dosing schedule, the goal will be to group the dose escalation cohorts. As a result, the following groupings of data will apply to table headers to summarize data in all demographic and safety tables:

- Fixed dose IV cohorts (cohorts 1 – 12)
- Step-dosing IV cohorts who received a single prime followed by the target dose (step cohorts 1, 301, and 302)
- Step-dosing IV cohorts who received two prime doses followed by the target dose (step cohorts 501 – 504)
- Fixed dose SC cohorts (cohort 701)

Summary tables will generally present the dosing cohorts as shown below.

Safety Tables

Parameter	Fixed IV	1 Prime Step IV	2 Prime Step IV	Fixed SC	Study Total
-----------	----------	-----------------	-----------------	----------	-------------

Specific study cohorts and treatment dose levels are as follows:

Study Part	Cohort Number	HPN424 Dose Levels
Dose Escalation Fixed Dosing IV	1	1.3 ng/kg IV
	2	4 ng/kg IV
	3	12 ng/kg IV
	4	24 ng/kg IV
	5	30 ng/kg IV
	6	40 ng/kg IV
	7	54 ng/kg IV
	8	72 ng/kg IV
	9	96 ng/kg IV
	10	120 ng/kg IV
	11	160 ng/kg IV
	12	150 ng/kg IV
Dose Escalation 1 Prime	1	12 / 36 ng/kg IV
	301	100 / 300 ng/kg IV

Study Part	Cohort Number	HPN424 Dose Levels
Step Dosing IV	302	75 / 225 ng/kg IV
Dose Escalation 2 Prime	501	100 / 300 / 450 ng/kg IV
	502	50 / 150 / 300 ng/kg IV (prior chemo)
	503	50 / 150 / 300 ng/kg IV (no prior chemo)
	504	50 / 150 / 450 ng/kg IV
Dose Escalation Fixed Dose SC	701	120 ng SC

Patients will be reported in their original dose cohort, regardless of any intra-patient dose escalation or dose changes. No patient on study received both IV and SC dosing.

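### SAP 7.1 labels every safety event with the starting dose cohort, so events after intra-patient escalation carry a lower dose than the one received

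*SAP*

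**What the plan says.** **Reporting rule.** SAP 7.1: "Patients will be reported in their original dose cohort, regardless of any intra-patient dose escalation or dose changes". The same section pools the cohorts into four columns for all demographic and safety tables: Fixed IV (cohorts 1 to 12, 1.3 to 160 ng/kg), one-prime step IV, two-prime step IV and Fixed SC. Listings are sorted by cohort.

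**When escalation is allowed.** Protocol 3.1.1.5: "Patients must have completed at least 2 cycles (6 doses) at their current dose level without intolerable toxicity". The new dose may be no higher than the highest level that the Cohort Review Committee (CRC) has already found safe. Protocol 3.1: "All patients will be administered HPN424 once weekly (QW) during 21-day cycles".

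**How long events are counted.** SAP 10.2 counts TEAEs from first dose to 28 days after last dose, and later still if related to study drug. SAP 10.5 uses the maximum post-baseline grade for laboratory shifts. Protocol 8.2, under Table 15, limits DLTs: "The DLT period for all patients in a given cohort will be through 21 days after the first Target Dose".

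**Display by dose.** Protocol 10.7: "For all patients, AE data will be listed by dose level cohort". SAP 10.2 also promises patient incidence by cohort. SAP 4.1 keeps safety and tolerability at increasing dose levels as the primary objective for Dose Escalation.

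**The concern.** A patient who starts at a low dose and tolerates six doses may be moved to a higher one. Under SAP 7.1, every later adverse event, laboratory grade, discontinuation and dose modification still appears against the starting cohort. For escalated patients the error runs one way: events at a higher dose are put on a lower-dose label. The rule treats dose reductions in the same way.

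The synoptic report concentrates on safety. Because the summary tables pool dose levels, the cohort-sorted listings are the main planned display in which a reader can relate toxicity to dose, and there the label is the starting dose. I found no rule in SAP 7.1 or 10.1 to 10.5, nor any item in the table and listing plan (13.1), that assigns an event to the dose at onset or marks a patient as escalated.

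**Working it through.** **Inputs.** Weekly dosing in 21-day cycles (Protocol 3.1); six doses at the current level before escalation (3.1.1.5); first Target Dose and DLT period by regimen (Table 15); expected treatment of about 28 weeks (3.3); late-DLT window of 60 days (5.2).

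**Step 1: reproduce the plan's calendar.** With k priming doses, the first Target Dose falls on day t = 1 + 7k and the DLT period ends on day t + 20. For k = 0, 1, 2, 3 this gives days 21, 28, 35 and 42, which match Table 15.

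**Step 2: earliest escalated dose.** I read the criterion as six doses at the Target Dose level, so the first escalated dose replaces the seventh weekly Target Dose, on day t + 42. The dosing window of -2 days could bring it up to two days earlier.

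| Priming doses | First Target Dose | DLT period ends | Earliest escalated dose |
|---|---|---|---|
| 0 (fixed) | day 1 | day 21 | day 43 |
| 1 | day 8 | day 28 | day 50 |
| 2 | day 15 | day 35 | day 57 |
| 3 | day 22 | day 42 | day 64 |

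The gap between the last two columns is 22 days in every row. Escalation cannot fall inside the 21-day DLT period, even with the two-day window.

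**Step 3: exposure that can carry the wrong label.** Protocol 3.3 says "patients are expected to remain on treatment for approximately 28 weeks", which is 28 × 7 = 196 days. For fixed dosing, 196 - 42 = 154 days can follow escalation, and 154/196 = 79%. With one prime it is (196 - 49)/196 = 75%, and with two primes (196 - 56)/196 = 71%. These are ceilings for a patient who escalates at the first opportunity. The number of patients escalated is not given, so no study-level figure can be computed.

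**Step 4: where the label shows.**
- *Within a pooled column.* An event moved from one Fixed IV cohort to another stays in the same column, so no table count changes.
- *Listings and by-cohort displays.* The event appears under the starting dose.
- *Across columns.* SAP 7.1 says no patient had both IV and SC dosing, so route is not confused. Movement from a fixed to a step regimen's dose level, or from one prime to two, is not excluded. Protocol 5.1.2.3 ties premedication to the safety data of the regimen being escalated to. Step cohort Target Doses reach 450 ng/kg against 160 ng/kg in Fixed IV.

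**Step 5: late DLTs, a separate protocol matter.** Protocol 5.2 defines these as DLT-grade events that "occur after the DLT period through the 60-day assessment period during Dose Escalation". The start of the 60 days is not stated. Counted from C1D1, the overlap between the post-escalation period and the window is 18, 11, 4 and 0 days for 0, 1, 2 and 3 primes. Counted from the first Target Dose, it is 18 days for every regimen. In fixed dosing this is days 43 to 60, or 18 of the 39 days from day 22 to day 60 (46%). Section 5.2 has the CRC review late DLTs belonging to the cohort under review, yet one of its options is: "Increase the number of patients at the dose level in which the late DLT occurred to satisfy the 3 + 3 decision rules". For an escalated patient, the cohort and the dose level of occurrence can differ, and the text does not say which governs.

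**The case against.** The best defence is that the planned tables compare dosing schedules, not dose levels. SAP 7.1 says so and pools accordingly. A reader might infer that the rule flattens or inverts a dose-toxicity relation in the summary tables. It does not, because moves within a column change no count. That part of the defence stands.

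A reader might also infer that a late DLT at the escalated dose would lead the lower, starting level to be declared above the MTD because of SAP 7.1. The documents do not support this:
- The SAP neither defines nor tabulates late DLTs. The CRC reviews them and chooses among several options, one of which is to continue enrollment at higher levels.
- Protocol 5.2 also points to the dose level where the event occurred.
- Escalation is limited to doses already cleared.
- The SAP is dated 03 March 2023, after the decision of 10 March 2022 to stop the study, so it could not have changed any dose decision.

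The timing is also a best case. In a leading fixed 3 + 3 cohort, the 48-hour stagger puts the second patient on day 3 and the end of that cohort's DLT period on day 23. A next cohort started on day 24 has its second patient on day 26 and finishes on day 46 at the earliest, so no higher level in that sequence is cleared by day 43. Day 43 applies where a higher level is already cleared, as in backfill.

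Finally, the information is obscured rather than lost: adverse event dates can be matched to the dosing records in Listing 16.2.5.1. That is true, but it leaves each reader to do the matching by hand, and it shows that the correction is cheap.

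**Conclusion.** The point holds as a reporting weakness in the SAP. Events after escalation are labelled with a dose lower than the one received, in the listings and in any by-cohort display. They would also sit in the wrong pooled column for a patient who moved to another regimen's dose level, which the documents leave open.

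Its size is unknown because the number of escalated patients is not stated. The 79% figure is an upper bound for one escalated fixed-dose patient. It rests on escalation at the first opportunity and on a 28-week expectation that Protocol 3.3 gives only for estimating study duration.

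It would be wrong to conclude that the primary DLT endpoint is biased: the DLT period ends before escalation is possible in every regimen. The late-DLT wording is a gap in Protocol 5.2 and does not follow from SAP 7.1.

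**What to change.** In SAP 7.1, 10.2 and 13.1:
- Keep the original cohort for DLTs and for events with onset before the first escalated dose.
- Derive dose at onset (the last dose given before onset) from the dosing data behind Listing 16.2.5.1. Add it, with an escalated-patient flag, to the AE, SAE and DLT listings (16.2.7.1 to 16.2.7.3).
- Show TEAEs with onset on or after the first escalated dose separately, by dose received, and state how many patients were escalated.

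The cost is one derived variable, one extra table and some SAP wording. The post-escalation group will be small and selected for having tolerated six doses, so its table should be read descriptively.

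Separately, the late-DLT passages in Protocol 5.2 should be reconciled for escalated patients, and the start of the 60-day window stated. This review does not propose which rule should apply.

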7.2 Definitions of Study Day, Durations, Baseline, and Post-Baseline Changes

Study day will be based on the date of administration of the first dose of HPN424 study treatment. Date calculations for any duration outcomes will be defined as follows:

- date of interest – first dose date + 1, when the date of interest is on or after the first dose date
- date of interest – first dose date, when the date of interest is before the first dose date

Study Day 1 is defined as the day the first dose of HPN424 study treatment is administered.

Duration outcomes will generally be reported in days. When necessary to convert to weeks, the duration in days will be divided by 7. When necessary to convert to months, the duration in days will be divided by 30.4375. When necessary to convert to years, the duration in days will be divided by 365.25.

Baseline will be based on the last non-missing value collected before or on the date (and time, if applicable) of the first dose of HPN424 study treatment. Post-baseline values will be those collected after the first dose of study treatment.

Change from baseline is defined as: post-baseline value – baseline value.

Percentage change from baseline is defined as:

$[(\text{post-baseline value} - \text{baseline value}) / \text{baseline value}] \times 100\%$

7.3 Imputation of Partial Dates and Missing Values

Data will not be imputed for analyses, with the exceptions noted below. These imputations will not change the raw data and will not change the data reported in listings. They will be used for analysis purposes only.

Date of diagnosis (years since initial diagnosis)

- If the year is missing, no imputation will be conducted.
- If the month is missing, the month will be set to January.
- If the day is missing, the day will be set to 1.

Adverse Events (to identify treatment emergence)

- If any part of the start date (month, day, year) is missing, no date imputation will be conducted. An adverse event (AE) with a partial date where the event could have occurred on or after the study treatment start date will be considered treatment emergent.

8 STUDY PATIENT DATA

8.1 Patient Enrollment

The number of patients treated by country and study site, including the name and institution of each investigator, will be summarized.

8.2 Patient Disposition

Patient disposition summaries will include the number of patients receiving study drug, the reasons for study treatment termination, the reasons for study discontinuation, and time on study in months.

8.3 Protocol Deviations

Protocol deviations will be identified by the Investigator and/or Harpoon as major and minor and classified by type before the database is locked. The patient incidence of major protocol deviations will be summarized for Safety Population overall and by the following major categories:

- inclusion and/or exclusion criteria (those who entered the study even though they did not satisfy the entry criteria)
- withdrawal criteria (those who developed withdrawal criteria during the study but were not withdrawn)
- study drug or dosing criteria not met (those who received the wrong treatment or incorrect dose or dosing error [modify as appropriate if only doses outside certain limits are considered major treatment deviations])
- concomitant medication/therapy (those who received a prohibited concomitant treatment)
- informed consent (those from whom informed consent was not properly obtained)
- deviations attributed to COVID-19

